3.3.3 Exclusion criteria

1. Major surgery (major according to the Investigator's and/or Medical Monitor's assessment) performed within 12 weeks prior to randomization or planned within 12 months after screening (e.g., hip replacement)
2. Presence of other active invasive cancers other than the one treated in this trial within 5 years prior to screening, except appropriately treated basal cell carcinoma of the skin, or *in situ* carcinoma of uterine cervix, or other local tumours considered cured by local treatment
3. Patients who must or wish to continue the intake of restricted medications (see Section 4.2.2.1) or any drug considered likely to interfere with the safe conduct of the trial
4. Previous administration of BI 891065 or BI 754091
5. Currently enrolled in another investigational device or drug trial, or less than 30 days since ending another investigational device or drug trial(s), or receiving other investigational treatments.

¹ A woman is considered of childbearing potential (WOCBP), i.e. fertile, following menarche and until becoming postmenopausal unless permanently sterile.

Permanent sterilisation methods include hysterectomy, bilateral salpingectomy and bilateral oophorectomy. Tubal ligation is NOT a method of permanent sterilisation.

A postmenopausal state is defined as no menses for 12 months without an alternative medical cause.

6. Patients who have been treated with any other anticancer drug within 4 weeks or within 5 half-life periods (whichever come earlier) prior to first administration of BI 891065. At least 7 days must have elapsed between the last dose of such agent and the first dose of study drug.
7. Persistent toxicity from previous treatments that has not resolved to \leq Grade 1 (except for alopecia and Grade 2 neuropathy due to prior platinum-based therapy)
8. Active, known or suspected autoimmune disease except vitiligo or resolved asthma/atopy
9. Interstitial lung disease
10. Any of the following cardiac criteria:
 - Mean resting corrected QT interval (QTcF) >470 msec
 - Any clinically important abnormalities (as assessed by the investigator) in rhythm, conduction, or morphology of resting ECGs, e.g., complete left bundle branch block, third degree heart block
 - Any factors that increase the risk of QTc prolongation or risk of arrhythmic events such as heart failure, hypokalaemia, congenital long QT syndrome, family history of long QT syndrome or unexplained sudden death under 40 years-of-age, or any concomitant medication with known or possible risk of QT interval prolongation
 - Patients with an ejection fraction (EF) $<55\%$ or the lower limit of normal of the institutional standard will be excluded. Only in cases where the Investigator (or the treating physician or both) suspects cardiac disease with negative effect on the EF, will the EF be measured during screening using an appropriate method according to local standards to confirm eligibility (e.g., echocardiogram [ECHO], multi-gated acquisition scan [MUGA]). A historic measurement of EF no older than 6 months prior to first administration of study drug can be accepted provided that there is clinical evidence that the EF value has not worsened since this measurement in the opinion of the Investigator or of the treating physician or both.
11. Out of range laboratory values are defined as:
 - Alanine transaminase (ALT) and aspartate amino transferase (AST) >3 times the ULN if no demonstrable liver metastases or >5 times ULN in the presence of liver metastases
 - Total bilirubin >1.5 times ULN, except for patients with Gilbert's syndrome who are excluded if total bilirubin >3.0 times ULN or direct bilirubin >1.5 times ULN
12. Human immunodeficiency virus (HIV) infection, acute or chronic viral hepatitis
13. Known hypersensitivity to the trial drugs or their excipients
14. Serious concomitant disease or medical condition affecting compliance with trial requirements or which are considered relevant for the evaluation of the efficacy or safety of the trial drug, such as cardiac, neurologic, psychiatric, infectious disease or active ulcers (gastro-intestinal tract, skin) or laboratory abnormality that may increase the risk associated with trial participation or trial drug administration, and in the judgment of the Investigator and/or Medical Monitor would make the patient inappropriate for entry into the trial.
15. Chronic alcohol or drug abuse or any condition that, in the Investigator's and/or Medical Monitor's opinion, makes them an unreliable trial patient or unlikely to complete the trial
16. Women who are pregnant, nursing, or who plan to become pregnant while in the trial and for at least 6 months after the last administration of trial medication.

17. Men who plan to father a child while in the trial and for at least 6 months after the last administration of trial medication.
18. Known presence of symptomatic central nervous system (CNS) metastases, unless asymptomatic and off corticosteroids and/or anti-convulsant therapy for at least 2 weeks prior start of treatment. Patients with asymptomatic CNS metastases may be enrolled following a 2-week washout period.
19. Patients receiving systemic treatment with any immunosuppressive medication within 1 week prior treatment start (steroids of max. 10 mg prednisolone equivalent per day are allowed, topical and inhaled steroids are not considered as immunosuppressive).
20. For Parts A and B: Patients with known epidermal growth factor receptor (EGFR), known anaplastic lymphoma kinase (ALK), or known ROS Proto-Oncogene 1 (ROS1) genomic tumour aberrations, unless disease has progressed following available EGFR or ALK targeted therapy (including osimertinib for EGFR T790M-mutated NSCLC)
21. Out of range lab values as defined:
 - Absolute neutrophil count (ANC) $<1.5 \times 10^9/L$ ($<1500/mm^3$)
 - Platelet (PLT) count $<100 \times 10^9/L$
 - Haemoglobin $<90 \text{ g/L}$ ($<9 \text{ g/dL}$)
 - Creatinine >1.5 times ULN (patients may enter if creatinine is $>1.5 \times \text{ULN}$ and estimated glomerular filtration rate (eGFR) $>30 \text{ mL/min/1.73 m}^2$) (Chronic Kidney Disease Epidemiology [CKD-EPI] Collaboration equation); confirmation of eGFR is only required when creatinine is $>1.5 \times \text{ULN}$.
22. For Part C: Patients with EGFR, ALK, or (if known) ROS1 genomic tumour aberrations
23. For Part C: Patients with any CTLA-4 therapy
24. For Part C: One or more lines of anti-cancer therapy between previous anti-PD-1/anti-PD-L1 mAb therapy and study entry.

3.3.4 Withdrawal of patients from therapy or assessments

Patients may potentially be withdrawn from trial treatment or from the trial as a whole (“withdrawal of consent”) with very different ramifications. Please see Section 3.3.4.1 and Section 3.3.4.2, respectively.

Every effort should be made to keep the entered patients in the trial: if possible on treatment, or at least to collect important trial data. Measures to control the withdrawal rate include careful patient selection, appropriate explanation of the trial requirements and procedures prior to entering the trial, as well as the explanation of the consequences of withdrawal. The decision to withdraw from trial treatment or from the whole trial as well as the reason must be documented in the patient files and CRF.

3.3.4.1 Withdrawal from trial treatment

An individual patient is to be withdrawn from trial treatment(s) if:

- The patient wants to withdraw from trial treatment, without the need to justify the decision.
- The patient needs to take concomitant drugs that interfere with the investigational product or other trial medication.

- The patient can no longer be treated with trial medication for other medical reasons (such as surgery, adverse events, other diseases, or pregnancy [see Section 5.2.6.8]).
- The patient has been non-compliant with important trial procedures and, in the opinion of both, the Investigator and Sponsor representative, is not willing or able to stick to the trial requirements in the future.
- Recurring radiologic progression. Note: In the case of initial radiological PD, patients will be allowed to stay on treatment if the following criteria are met:
 - The Investigator feels that it is in the patient’s best interest
 - The patient signed an informed consent form specific for this circumstance after acknowledging that this practice is not considered standard in the treatment of cancer. The specific informed consent process for this circumstance includes discussion of alternative treatment options, including any available approved therapies (if applicable) and participation in alternative clinical trials.
 - Absence of clinical symptoms or signs indicating clinically significant PD
 - No decline in performance status
 - Absence of rapid PD or threat to vital organs or critical anatomical sites (e.g., central nervous system metastasis, respiratory failure due to tumour compression, spinal cord compression) requiring urgent alternative medical intervention
 - No significant, unacceptable, or irreversible toxicities related to study treatment.
- A pause of treatment or delayed start of treatment of more than 12 weeks due to SAEs/AEs
- The following adverse event(s) occur:
 - Cytokine release syndrome CTCAE Version 5.0 (R18-1357) Grade 3 or 4
 - Immune related AEs requiring permanent study drug discontinuation as described in Guidelines for Management of Immune-Related AEs (Appendix 10.2):
 - Grade 3 to 4 pneumonitis
 - Grade 3 to 4 adrenal insufficiency
 - Grade 4 diabetes mellitus
 - Any grade encephalitis
 - Grade 4 hypophysitis
 - Grade 4 rash
 - Grade 3 to 4 colitis or recurrent colitis of any grade
 - Any recurrent Grade 3 to 4 AE
 - Transaminase increases >5 times ULN or total bilirubin >3 times ULN
 - Inability to taper steroids to 10 mg or less prednisone or equivalent within 12 weeks
 - SAEs/AEs of Grade ≥ 2 deemed intolerable by the patient or the treating physician and not responding to medical management and any SAEs/AEs of \geq Grade 3 that do not recover to Grade 1 or less within 12 weeks
 - Persistent Grade 2-3 AEs that do not recover to Grade 1 or less within 12 weeks
 - Grade 3 to 4 AEs that are classified as immune-related by the Investigator but are not listed in Appendix 10.1 if they do not resolve to Grade ≤ 1 or baseline with immunosuppressive therapy within 2 weeks.

- \geq Grade 4 drug-related AEs.

Given the patient's agreement, the patient will undergo the procedures for early treatment discontinuation and will be followed up as outlined in [Part A Flow Chart](#), [Part B Flow Chart](#), [Part C Lung Flow Chart](#), and Section 6.2.3.1. For all patients the reason for withdrawal from trial treatment (e.g., adverse events) must be recorded in the CRF. These data will be included in the trial database and reported.

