 - For Grade 2 hypothyroidism, consider withholding BI 754091 and BI 891065
 - For Grade 3-4 hypothyroidism, withhold BI 754091 and BI 891065, consider admission and IV therapy, especially in case of myxedema
 - BI 754091 and BI 891065 may be restarted once symptoms resolve to baseline with appropriate thyroid hormone supplementation
- Primary hyperthyroidism
 - For Grade 1 hyperthyroidism, BI 754091 and BI 891065 may be continued , with regular monitoring of thyroid values.
 - For Grade 2 hyperthyroidism, consider withholding BI 754091 and BI 891065, initiate therapy as per available guidelines.

- For Grade 3-4 hyperthyroidism, withhold BI 754091 and BI 891065. Consider hospitalization, especially in case of thyrotoxicosis.
- BI 754091 and BI 891065 may be restarted once symptoms resolve to baseline.

Note: in case of concomitant adrenal dysfunction, this must be corrected first, prior to thyroid hormone replacement (reduced stress tolerance)

Adrenal insufficiency

- Interruption of BI 754091 and BI 891065 therapy should be considered for adrenal insufficiency grade 1 or 2, and is warranted for grade 3 and grade 4 adrenal insufficiency, until patient is stabilized on hormone replacement therapy.
- Therapy with BI 754091 and BI 891065 may be restarted once stable replacement therapy has been achieved.
- Note: in case of concomitant hypothyroidism, steroid replacement therapy should precede thyroid hormone substitution to avoid adrenal crisis.

Hypophysitis:

- Diagnostic workup for hypophysitis should be considered e.g. for patients with multiple endocrinopathies, unexplained fatigue, new severe headaches or vision changes.
- Patients should be appropriately advised regarding potentially reduced stress tolerance and increased substitution demands e.g. in case of infections, and to wear a medical alert bracelet to inform medical personnel about potentially increased hormone demands in situations of stress, in case of emergencies.
- Interruption of BI 754091 and BI 891065 therapy should be considered for Grade 1 or 2 hypophysitis, and is warranted for Grade 3 and higher hypophysitis, until patient is stabilized on hormone replacement therapy.

Hepatitis:

- Work-up for other causes of elevated liver enzymes, see also section on potential DILI.
- For Grade 1 hepatitis (elevated AST/ALT < 3x ULN and/or total bilirubin <1.5x ULN), BI 754091 and BI 891065 may be continued, close monitoring of liver values is warranted.

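### Section 3.3.4.1 mandates permanent discontinuation by reference to Appendix 10.2, but the appendix allows restart for some of the same events, and no passage says which text prevails

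*Protocol*

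**What the plan says.** Section 3.3.4.1 sets out when a patient must be withdrawn from trial treatment. One item is "Immune related AEs requiring permanent study drug discontinuation as described in Guidelines for Management of Immune-Related AEs (Appendix 10.2"), followed by named events. Four of these matter here: "Grade 3 to 4 adrenal insufficiency", "Grade 3 to 4 colitis or recurrent colitis of any grade", "Grade 4 diabetes mellitus" and "Grade 4 hypophysitis". The section ends with a further criterion for events at or above "Grade 4 drug-related AEs".

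Appendix 10.2 treats the same events differently. On adrenal insufficiency it says that interruption "is warranted for grade 3 and grade 4 adrenal insufficiency, until patient is stabilized on hormone replacement therapy", and then that "Therapy with BI 754091 and BI 891065 may be restarted once stable replacement therapy has been achieved". Its own list of events requiring permanent discontinuation includes colitis only at Grade 4 or on recurrence, and its colitis paragraph lets restart be considered after Grades 1 to 3. Its general principles describe restart as commonly possible for endocrine immune-related events whatever the grade.

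Both texts are in the body of protocol Version 7.0. The amendment log plays no part in the comparison.

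**The concern.** Section 3.3.4.1 presents its list as a restatement of the appendix, and it is not one. An investigator whose Part B patient has Grade 3 colitis or Grade 3 adrenal insufficiency finds one passage that requires permanent discontinuation and another that allows treatment to resume after recovery or stabilisation. Two sites could act in opposite ways on the same event, and each could cite the protocol.

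At stake are patient safety after a severe immune-related event and consistent conduct across sites. For Grade 3 immune-related events the appendix only recommends medical-monitor agreement before restart, so that safeguard lowers the risk without removing it.

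**Working it through.** No formula applies and the plan states no figure to reproduce. The check sets the current texts side by side.

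**Step 1: the event-specific entries.** Section 3.3.4.1 names eight: pneumonitis, adrenal insufficiency, diabetes mellitus, encephalitis, hypophysitis, rash, colitis, and the transaminase/bilirubin thresholds. Four agree with Appendix 10.2: pneumonitis, encephalitis, rash, and transaminase/bilirubin. The other four do not:

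| Event and grade | Section 3.3.4.1 | Appendix 10.2 | Basis of the conflict |
|---|---|---|---|
| Adrenal insufficiency, Grades 3 and 4 | Permanent | Interrupt until stable on replacement; restart then allowed | Face of the texts |
| Colitis, Grade 3 | Permanent | Withhold and treat; restart can be considered after improvement to Grade 1 or below; permanent only at Grade 4 or on recurrence | Face of the texts |
| Diabetes mellitus, Grade 4 | Permanent | The paragraph covers new-onset Type 1 diabetes with no grade limit; withhold, then restart allowed once insulin gives stable control | Face of the texts |
| Hypophysitis, Grade 4 | Permanent | Interrupt at Grade 3 and above until stable on replacement; no restart sentence of its own | Needs the general endocrine rule |

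The event-and-grade combinations number 2 + 1 + 1 + 1 = 5. Four rest on the face of the texts and one (hypophysitis) on a joint reading. Two are Grade 3 (adrenal insufficiency, colitis) and three are Grade 4 (adrenal insufficiency, diabetes, hypophysitis).

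**Step 2: the Grade 4 criterion.** Restart text in the appendix's own paragraphs reaches Grade 4 for six event types: hyperglycaemia with ketosis, hypothyroidism, hyperthyroidism, adrenal insufficiency, inflammatory arthritis, and polymyalgia-like syndrome. Where such an event is drug-related, Section 3.3.4.1 requires withdrawal and the appendix allows resumption. The Grade 4 combinations in Step 1 fall under the same criterion if drug-related; the two Grade 3 combinations rest on the list alone.

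**Step 3: the other direction.** The appendix's permanent list has 17 bullets, of which 3 are general, leaving 17 − 3 = 14 that are event-specific. Nine of these contain 15 event types that must stop below Grade 4 and that Section 3.3.4.1 does not name, such as myocarditis of any grade and nephritis at Grade 3 or higher. That is a count of names, not of gaps. General bullets in Section 3.3.4.1 (recurrent Grade 3 to 4 events, no recovery within 12 weeks, drug-related events of Grade 4 or higher) cover part of it. They do not cover, for example, low-grade myocarditis, or a first Grade 3 nephritis, that recovers within 12 weeks.

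**Step 4: which text governs.** Footnote a of the Part A and Part B flow charts, the closing part of Section 4.1.7, and Section 6.2.2 all point to Section 3.3.4.1. The opening of Section 4.1.7 sends immune-related events to Appendix 10.2, and Section 3.3.4.1 itself defers to the appendix. No passage gives an order of precedence.

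**The case against.** The strongest reply is that Section 3.3.4.1 governs in practice. It is mandatory, more cross-references lead to it, and the appendix calls its guidance limited and words restart as permission. An investigator who withdraws the patient breaches neither text. This shows that the cross-references are not evenly balanced, but it does not settle the matter. Section 3.3.4.1 justifies its list by what the appendix describes, and the appendix describes something else. Nor is either list the stricter one throughout: Section 3.3.4.1 is stricter for colitis and adrenal insufficiency, the appendix for myocarditis and nephritis.

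The appendix also says that most Grade 4 immune-related events warrant permanent discontinuation. That leaves room for exceptions, and its next bullet makes one for endocrine events. Its clause on discussing rare continuation with the sponsor concerns going on despite guidance to stop permanently; for the events in Step 1 the appendix does not itself give that guidance.

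Four stronger readings are tempting and are not supported:

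- A reader might infer that the events named only in the appendix are a second contradiction. They are omissions: the lead-in in Section 3.3.4.1 can be read as importing them, so stopping for myocarditis complies with both texts.
- A reader might infer a further conflict on infusion reactions of Grade 3 or higher, because Section 4.1.7 stops both drugs and Section 5.2.6.4.2 names BI 754091 only. Section 4.1.7 bridges this with its general rule that both drugs are stopped together in Parts B and C.
- A reader might infer that the SAP analyses are affected through deviation code C3. That code is checked manually, excludes no one, and already reaches both lists through Section 4.1.7. It only inherits the ambiguity.
- A reader might infer an effect on MTD evaluability. Section 3.3.4.4 governs that, and nothing in the documents shows a patient whose evaluability turned on this difference.

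**Conclusion.** The contradiction is real and should be removed. Its core is three entries that conflict without inference (adrenal insufficiency at Grades 3 and 4, colitis at Grade 3, diabetes mellitus at Grade 4), plus hypophysitis at Grade 4 on a joint reading: four of eight event-specific entries. The conflict between the Grade 4 criterion and the restart text for six event types is conditional on the event being drug-related. The unnamed events in the other direction are a secondary matter of completeness.

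The reach is mainly Part B. Section 5.2.6.4.4 ties immune-related events to immunotherapy, Part A gives BI 891065 alone, and SAP Section 4 states that Part C was cancelled with no patients enrolled. The conclusion rests on the wording alone; it assumes nothing about how often these events occur and takes no view on which rule is clinically right.

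**What to change.** Reconcile Section 3.3.4.1 and Appendix 10.2 event by event so that one list governs permanent discontinuation and the other text only refers to it. Decide in the same pass whether the events named only in the appendix belong on that list. State how the criterion for drug-related events of Grade 4 or higher relates to the appendix's restart text. As a follow-on, have SAP deviation code C3 cite the governing list. The sponsor's medical team decides which clinical rule applies to each event.

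The cost is protocol and SAP wording only; no new data or analysis is needed.

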3.3.4.2 Withdrawal of consent for trial participation

Patients may withdraw their consent for trial participation at any time without the need to justify the decision. This will however mean that no further information may be collected for the purpose of the trial and negative implications for the scientific value may be the consequence. Furthermore it may mean that further patient follow up on safety cannot occur.

If a patient wants to withdraw consent, the Investigator should explain the difference between treatment withdrawal and withdrawal of consent for trial participation and explain the options for continued follow up after withdrawal from trial treatment (see Section 3.3.4.1).

3.3.4.3 Discontinuation of the trial by the Sponsor

Boehringer Ingelheim reserves the right to discontinue the trial overall or at a particular trial site at any time for the following reasons:

- Failure to meet expected enrolment goals overall or at a particular trial site
- Emergence of any efficacy/safety information invalidating the earlier positive benefit-risk-assessment that could significantly affect the continuation of the trial
- Violation of Good Clinical Practice (GCP), the trial protocol, or the contract, impairing the appropriate conduct of the trial.

The Investigator / the trial site will be reimbursed for reasonable expenses incurred in case of trial termination (except in case of the third reason).

3.3.4.4 Replacement of patients who have received at least one dose of BI 891065 or BI 754091

Replaced patients will not be evaluated for the MTD determination, and an additional patient will be entered at the same dose level. The following patients may be replaced:

- Patients who permanently discontinue treatment during treatment Cycle 1 of Part A or Part B for reasons other than a DLT, unless they develop a DLT.
- Patients who have missed more than 5 doses of BI 891065 in the first treatment cycle of Part A or Part B, unless they develop a DLT.
- Patients who have reduced BI 891065 dose level during treatment Cycle 1 Part A or Part B, unless they develop a DLT.
- Patients who have taken less than 80% of the BI 891065 overall dose during treatment Cycle 1 of Part B, unless they develop DLT.

- Patients who have received less than 50% of a BI 754091 initial dose of Part B, unless they develop a DLT.
- Patients who miss 2 or more partial or complete visits of the first cycle of Part A or Part B and (after discussion between the Sponsor and the Investigator) if the information needed to assess PK/PDc and safety parameters (including evaluation for DLTs), unless they develop a DLT.

Patients who permanently discontinue treatment because of a DLT will not be replaced.

Patients in the NSCLC expansion cohort (Part C) will not be replaced unless it becomes apparent that probably less than 40 patients will be evaluable for the assessment of the primary endpoint. In such a case, patients of the NSCLC expansion cohort concerned may be replaced only after confirmation of the Sponsor in writing.

